11.1. General information

Only clinical centres with the Intrabeam® or those who are able to refer patients to such a centre may

enter the trial. Centres with newly acquired equipment must consult the TARGIT Trial Operations

Centre prior to entering patients into the trial. A minimum of Five "pilot" cases (non-randomised

patients suitable to receive TARGIT) will be performed followed by an audit by a member of the

Steering Committee (or an appointed delegate). A confirmation of the quality control of the system

set up must be received at the Operations Centre before randomisation can begin.

Surgery: All patients will have local excision of the primary tumour following appropriate clinical

work-up. No special assessments prior to randomisation will be required although mammography and

ultrasound are recommended.

Surgery will be according to usual local practice but complete macroscopic excision of the tumour is

required. The aim of the local excision should be to achieve the widest margin of excision whilst

maintaining a good cosmetic outcome (aim for margins of >10mm). The final histological margin

should be at least 1mm clear of all invasive and in-situ disease, or 'no ink on margin' as per local

practice. For superficial tumours an ellipse of overlying skin should be excised. The depth of

resection will depend on the position of the tumour within the breast and the size of the breast but in

most instances will extend to the pectoral fascia. The exact size of the tumour free margin and

specimen weight will be recorded to assess equality between the two groups.

In all patients, but especially in those women with impalpable tumours where pre-operative

localisation has been performed, the specimen should be well orientated with sutures or clips

according to local protocols and x-rayed intra-operatively. The specimen x-ray should be examined

in theatre to ensure complete excision of the lesion and to help with the assessment of adequacy of

the margins. Further tissue should be taken (and marked) from a margin if the x-ray abnormality

extends near the margin.

Either a standard sentinel node biopsy or at least level II axillary lymph node dissection must be

performed in all patients. Similar surgical techniques must be employed in all patients regardless of

the randomisation. Wound closure must be performed meticulously (air and water-tight) as described

⁹ ¹⁸ and sutures (if non-absorbable), should remain in place for 14 days.

Patients who are not randomised to the TARGIT arm should have the tumour bed localised with two

titanium clips in each available face (posterior. medial/lateral, superior and inferior) before closure

of the skin.

TARGIT B Protocol IRAS No: 77045

Version 6.0, Dated 10/09/2018

Page 22 of 46

11.2. Use within the trial

Patients with positive margins: If final pathology shows involved or close margins (evidence of

invasive or in situ tumour at, or within 1mm, of an excision margin or 'ink-on-margin' as per local

practice and multidisciplinary team discussion) re-excision is strongly recommended. In some cases,

this may necessitate a mastectomy. Decision about re-excision or mastectomy should not be

influenced by whether the patient had received TARGIT-Boost or not. For patients who have already

received TARGIT, such re-excision to clear margins should be followed by external beam

radiotherapy excluding the boost. Intraoperative radiotherapy or EBRT boost of the re-excised tumour

bed which had previously received TARGIT should not be done because we have had no experience

regarding its safety.

The procedure for delivering the TARGIT is described below, including the administration of a

prophylactic antibiotic just after the induction of anaesthesia. In this group of patients, special care

should be taken to ensure the wound closure is meticulous, air- and water-tight and sutures are not

removed for at least 2 weeks. If an absorbable suture is used it should be at least 3-0 in thickness,

should not be absorbable within 2 weeks and Steristrips should be used and left in situ for 2 weeks.

Also, in this group the antibiotic cover should be for 5 days.

Pathological Examination: Data from pathological examinations should be recorded on the

appropriate data collection forms and all reporting of pathological findings are to be in accordance

with the TNM Classification.

Radiotherapy

TARGeted Intra-operative radioTherapy (TARGIT): The technique of the operation and the delivery

of radiotherapy have been described in a video available from the TARGIT Trial Operations Office

and at http://www.youtube.com/watch?v=GVlHGpvRf8A. We have established a standard training

protocol before any centre is allowed to recruit into the trial. We shall ensure that the doses are

standardized between all centres.

Preparation of the Intrabeam: TARGIT will either be delivered in the operating theatre immediately

after the removal of the tumour or as a subsequent procedure, a short time later. The procedure has

been described in detail ^{8 9 18}. The device and the arm of the stand are wrapped in a sterile clear plastic

cover. The individual applicators are sterilised prior to the theatre session. The size of the sphere is

determined at surgery by the surgeon and/or the radiation oncologist. An appropriately sized

TARGIT B Protocol IRAS No: 77045

Version 6.0, Dated 10/09/2018

Page 23 of 46

Intrabeam applicator fits comfortably without tension in the surrounding tissue so that the skin and

subcutaneous tissues can be gathered with a purse string suture over the sphere. Any other apparatus

to assist this apposition may also be used.

It is essential that complete haemostasis is achieved before insertion of the applicator sphere, because

even a small ooze of blood can distort the cavity around the sphere and significantly change the target

dose. The applicator sphere is inserted into the surgical cavity and a deep surgical purse string suture

is inserted in the breast tissues to bring together the target breast tissue so that it applies well to the

surface of the Intrabeam applicator sphere and holds it in place during treatment. The skin, but not

the breast tissue, can be slightly everted and held away from the delivery device by surgical sutures

to prevent direct contact with the sphere. It is important to keep the skin at a distance of at least 1cm

from the applicator. However, at no point should anything (such as a piece of gauze) be placed

between the target breast tissue and the applicator surface thus making sure not to inadvertently shield

the areas of tissue that require radiation treatment. If the skin is coming too close then it may need to

be excised. Also the breast tissue should not be dissected off the skin as it could reduce its blood

supply reducing the effectiveness of radiotherapy. The tumour bed should have no or minimal

disturbance.

If necessary, protective caps (made from tungsten impregnated rubber available from Carl Zeiss) may

be fashioned by the surgeon to protect deep or superficial structures. If the deep margin of excision

is such that left anterior descending branch of the coronary artery could receive significant radiation

dose, then the surface of the applicator sphere should be covered with a protective cap at the chest

wall. However, in most patients the normal thickness of the chest wall (muscle and rib cage) would

provide adequate shielding and such a protective cap is not required.

TARGIT Dose Prescription and Delivery: The surgeon and radiation oncologist should choose the

largest possible suitable applicator in order to ensure the highest dose is delivered to the tumour bed

tissue. Radiation protection shielding material may also be used, which is sterile and suitable for both

internal and external use.

A dose of 20Gy (in water) calculated at the applicator surface should be prescribed by the radiation

oncologist and delivered to the breast tissue. This takes typically 30 minutes depending on the size of

the applicator. This dose has superior radiobiological advantages as it ensures that tumour beds from

larger tumours receive a higher dose than small tumours ^{19 20}.

During the radiation treatment, the anaesthetist, clinician and physicist may remain in the room. To

avoid unnecessary exposure we recommend that as many people as possible vacate the operating

theatre and those remaining, either wear a lead apron or remain behind a shielded screen. It is

important to emphasise that the operation theatre itself needs to be initially checked that its walls

Page 24 of 46

provide adequate shielding for radiation- although this does not need to be more than that required

for routine operative fluoroscopy.

Completion of TARGIT: After completion of radiation, the conforming stitches are removed. Strict

haemostasis should be obtained following the removal of the Intrabeam device. The skin is sutured

meticulously to achieve a water-tight closure and a good cosmetic result. If non-absorbable- sutures

are used, they should be left in situ for 14 days and if absorbable sutures are used, Steristrips covering

the entire wound should be left in place for 14 days ⁹.

TARGIT Physics: Prior to entering any patient into the trial, centres will be expected to submit data

for each x-ray source (XRS) probe and applicator set in use. Each centre will be responsible for

measuring data for the probe and applicator set, and shall submit the data supplied by the

manufacturer for comparison with measured data together with a copy of the letter of acceptance

supplied by Carl Zeiss.

External beam radiotherapy: Planning protocols for the conventional whole breast radiotherapy will

vary from centre to centre but for each centre a written policy will be required and should follow

acceptable protocols (e.g., 40Gy in 15 fractions or 50Gy in 25 fractions). Patients with previously

irradiated adjacent fields for example, those with previous contra-lateral breast cancer, will need to

have the radiotherapy fields modified according to local policies. EBRT tumour bed boost should

only be delivered to those patients who are randomised to the EBRT boost arm and they should

preferably receive this in the form of 16Gy in 8 fractions over 1.5 weeks with electrons of appropriate

energy². We believe that external beam radiotherapy planning should be image guided using tumour

bed localisation clips as described in the IMPORT trials ²¹. Although a centre would not be excluded

from the study if this is not being practised (as stratification of randomisation will balance the two

arms), we shall strongly recommend its use. VBH or a similar technique can be used to reduce

exposure of internal organs to unnecessary radiation.

Adjuvant Systemic Therapy: Trial patients may be recommended appropriate adjuvant systemic

therapy according to local practice or trial protocols. The sequencing of these other therapies is not

governed by this protocol, but the policy for such treatment-sequencing should be declared in the

Policy Statement (e.g. it should be declared whether the EBRT will be delivered before or after

chemotherapy).

Patient Compliance: Compliance is likely to be high because the treatment is given during

surgery. Some patients will refuse the allocated therapy between randomisation and surgery, but

[figure not shown]
based on our experience with more than 3000 patients from the TARGIT A Trial we think the number

will be minimal.

TARGIT B Protocol IRAS No: 77045

The Technology

The recent development of a new method has made possible the delivery of radiation directly to the tissues at the site of the primary tumour. The Intrabeam® (originally developed by the Photoelectron Corporation in Massachusetts, USA, but now manufactured by Carl Zeiss, Germany) is a simple but ingenious device, in essence a miniature electron beam-driven X-ray source which provides a point source of low energy X-rays (50kV maximum) at the tip of a 3.2mm diameter tube. The radiation source can be inserted into the area of interest immediately after excision of the tumour (Figure 1) and switched on for 20-35 minutes to provide intra-operative radiotherapy accurately targeted to the tissues that are at highest risk of local recurrence. The physics, dosimetry and early clinical applications of this soft x-ray device have been well studied and the probe has already been used for treatment of human malignant brain tumours. ^{8 9 22}

Figures 1 (a) and (b)

Figure 1 (a): The applicator being placed in the tumour bed, immediately after the excision of the tumour.

Figure 1 (b): The x-ray source is delivered to the tumour bed utilizing a surgical support stand. The sterile applicator is joined with a sterile drape that is used to cover the stand during treatment delivery.

It was developed for use for breast cancer and was first piloted at University College London ^{8 18 23}. The device has subsequently received FDA approval for use in any part of the body. For use in the breast, the radiation source is surrounded by a spherical applicator (see Figures 1 (a) and 2). The spherical applicator is specially designed to produce a uniform field of radiation at its surface, enabling delivery of an accurately calculated dose to a prescribed depth. It is inserted in the tumour bed and apposed to it with surgical sutures and/or other means. Since the radiation consists of soft X-rays, the beam rapidly attenuates reducing the dose to more distant tissue. Full measurements and calibration are carried out in a water phantom and/or in materials that simulate the radiation absorption properties of the breast. Depending upon the size of the surgical cavity, various sizes of applicator spheres are available. The radiation received is proportional to the time the machine is

switched on. The precise dose rate depends on the diameter of the applicator and the energy of the beam, both of which may be varied to optimise the radiation treatment. For example, a dose of about 20Gy can be delivered in about 20 minutes to the tumour bed apposing the applicator. Following the treatment delivery, the radiation is switched off, the applicator removed from the wound, and the wound closed in the normal way.

The x-ray source is small and lightweight (weight =1.8 Kg; dimensions: X-ray generator body 7 x 11 x 14 cm; applicator: 16 cm long conical applicator shank with a 2 to 5 cm sphere at the tip) and is mounted on the surgical stand and balanced for ease of delivery and support during treatment. With this elegant approach the pliable breast tissue around the cavity of surgical excision wraps around the radiotherapy source, i.e. the target is 'conformed' to the source. This simple, effective technique avoids the unnecessarily complex and sophisticated techniques of using interstitial implantation of radioactive wires to provide high dose radiotherapy to the tumour bed or the even more complex techniques necessary for conformal radiotherapy by external beams from a linear accelerator. The quick attenuation of the radiation dose allows the treatment to be carried out in the routine theatre. The walls usually incorporate shielding for microwave radiation from electronic equipment such as mobile phones and as such provide enough protection to the staff. Furthermore, the dose attenuates rapidly, so that the highest radiation dose is received by tissue nearest the primary tumour and a much lower dose at the skin. Thus in theory, the biological effect and cosmetic outcome could be improved.

[figure not shown]

Figure 2: The Intrabeam System (PRS). The electrons are generated and accelerated in the main unit and travel via the electron beam drift tube which is surrounded by the conical applicator sheath such that its tip lies at the epicentre of the applicator sphere. Once the electrons hit the inner surface of the hemisphere at the tip, x-rays are generated. Thus a uniform radiation dose rate is available at the surface of the applicator sphere ⁸. The details of operative technique are available at http://www.targit.org.uk.

12. Randomisation

Randomisation schedules will be prepared using a bespoke SAS program, blocked and stratified by centre and stratum, with equal allocation between treatment arms, by the Trials Operations Office. The schedules will be accessible by authorised staff only. Requests for randomisation can be made by either fax (receipt of a completed inclusion/exclusion criteria checklist) or telephone. A trained member of staff will confirm eligibility and perform the randomisation, according to the Standard Operating Procedure. The turnaround time for faxed randomisations is next working day, for telephone randomisations immediate provided the call is made between 09.00 and 17.30 UK time.

The randomisation codes will be included in the data sent to the Trial Statistician for analysis.

13. Blinding & other measures taken to avoid bias

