We first proposed this study in 2005. Since then the (IMPORT- High) study is being planned in the UK to test whether a higher tumour bed dose reduces local recurrence in high risk patients. However, our study is unique in terms of the localisation and timing of delivery of tumour bed boost and may achieve a better tumour control because of the reasons explained above. The Milan group is now planning to test whether intraoperative boost using the ELIOT technique may yield superior outcome. The ELIOT technique could in theory suffer from the problem that the high dose of radiotherapy (20Gy) is delivered in a very short time (2-4 minutes) and the long term cosmetic or toxicity of such an approach is not yet known. The longer duration (25-30 min) of radiotherapy during the TARGIT intra-operative procedure, in theory, would allow for repair of DNA damage by normal tissues (but not tumour cells), thus reducing long term toxicity. This theoretical concept has been vindicated by our long term toxicity and local recurrence outcome data. Hence the TARGIT-B trial remains unique and will address a very important question and could potentially provide a better clinical outcome.

7. Trial objectives and purpose

This is a randomised controlled trial that compares two treatments in patients with early breast cancer

who have undergone local excision of a breast cancer and face a relatively higher risk of local

recurrence. The conventional policy for such a patient is to receive radiation boost to the tumour bed

delivered by external beam radiotherapy (EBRT) in addition to whole breast EBRT according to local

treatment guidelines. The experimental policy is to give targeted intra-operative radiotherapy

(TARGIT-Boost) in a single dose to substitute for the usual boost dose.

Primary Objective: To evaluate whether a tumour bed boost in the form of a single fraction of

radiotherapy given intra-operatively and targeted to the tissues at the highest risk of local recurrence

is superior (in terms of local tumour control) to standard post-operative external beam radiotherapy

boost, after breast conserving surgery in women undergoing breast conserving therapy who have a

higher risk of local recurrence.

Secondary Objectives: To compare the treatment arms with respect to site of relapse within the breast;

relapse-free survival and overall survival (breast cancer and non-breast cancer deaths –such as cardiac

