and other cancers), local toxicity/morbidity, cost-effectiveness and quality of life.

Separate sub-protocols, not included in this protocol, will address other endpoints, including cosmetic

outcome, cardiopulmonary toxicity, patient satisfaction and patient preference. These sub-protocols

will be subject to their own sponsorship and regulatory reviews.

TARGIT B Protocol IRAS No: 77045 Version 6.0, Dated 10/09/2018 8. Study design

Core Protocol: This pragmatic, parallel group, superiority randomised trial is designed to directly

compare the outcome, primarily in terms of local control, of two approaches of adjuvant radiotherapy.

Patients selected for breast-conserving surgery who are considered to have a high risk of local

recurrence are eligible to participate in the trial once they have received information and given their

consent.

Individual centres may choose to recruit only a subset of patients eligible as per the entry and

management criteria given in the protocol; for example some centres may decide not to enter patients

who require a second procedure solely to give the TARGIT-boost. These policies are to be

documented in advance and all trial patients treated according to this pre-declared policy. The study

will be analysed under an 'intention to treat policy' (ITT) with stratified analyses performed.

This trial allows entry of patients who are suitable, (or have been rendered suitable by neoadjuvant

systemic therapy) to be treated by breast conserving therapy and who are expected to have a high risk

of local recurrence, (young age, grade III histology, lymphovascular invasion, grossly involved

axillary nodes, etc.), or risk of recurrence in other quadrants of the breast such as extensive intraduct

component (EIC) or lobular carcinoma. Preferably, tumours should not be more than 4 cm in size, as

the largest applicator size is 5cm. Patient consent is sought and randomisation is carried out prior to

the surgical removal of the tumour. After wide local excision of the tumour, a tumour bed boost is

delivered using the Intrabeam system as described previously in the patients who are randomised to

TARGIT Boost. Those randomised to EBRT boost will have this boost delivered by conventional

External Beam Radiation Therapy (EBRT).

Most patients who require treatment for a metachronous breast cancer are excluded from entry to

trials of local treatment. Although there are good reasons for this, later development of recurrence

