Simple cost diaries will be sent to each patient after randomisation, these instruments will be sent out by the TARGIT Trials Office and returned to the TARGIT Trials Office. Cost data will be collected only during the first three years of the study. Please see questionnaire schedule for data collection points. Diaries will be sent out at the beginning of the appropriate time window.

Questionnaire Schedule:

	Baseline (before surgery)		6	12	18	24			36	48	60
EQ5D &	√ V		V	V	√	V			$\sqrt{}$	V	√
FACTB+4											
		0-3	3-6	6-12	12-18	18-24	24-30	30-36			
Cost diary		1	1	V	$\sqrt{}$	1	V	$\sqrt{}$			

9. Subject selection

The trial will accrue from the centres already participating in the TARGIT-A trial, although many more centres are keen to participate. The TARGIT-A trial accrued patients from around the world (21% from UK, 56% from Europe, 13% from Australia and 10% from North America) but both the trials have been conceptualized, designed, initiated, administered and published from the UK. With the trial inclusion criteria being selective for high risk women, we conservatively estimate the accrual rate to be 5 patients per week (250 per annum) after one year.

Inclusion criteria

Patients diagnosed with breast cancer and suitable for conserving surgery and whole breast radiotherapy, with a histological confirmation of carcinoma can be included in the study once a written informed consent is obtained. All patients should be available for regular follow-up (according to local policies) for at least ten years.

At least one of these criteria must be satisfied:

- 1. Less than 46 years of age
- 2. More than 45 years of age and with one or more of the following poor prognostic factors:
 - a) Grade 3
 - b) ER and/or PgR negative
 - c) lobular carcinoma
 - d) extensive intraductal component (EIC)
 - e) lymphovascular invasion
 - f) axillary nodal involvement
 - g) more than one tumour in the breast but still suitable for breast conserving surgery through a single specimen
 - h) any factor or a combination of factors that puts the patient at a higher risk of local recurrence as per the current local guidelines: e.g., those who need a tumour bed boost or those *not* suitable for TARGIT-Alone as standard treatment.
- 3. Those patients with large tumours which have responded to neo-adjuvant chemo- or hormone therapy that is given in an attempt to shrink the tumour, and are now suitable for breast conserving surgery as a result.

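### The EBRT boost is reserved by allocation with no fallback, so a woman allocated to TARGIT who never receives it would, as written, get no tumour-bed boost

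*Protocol*

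**What the plan says.** The rule is in Protocol section 11.2, under External beam radiotherapy. The sentence opens "EBRT tumour bed boost should" and continues "only be delivered to those patients who are randomised to the EBRT boost arm and they should", after which it gives the preferred dose and fractionation. It attaches no exception.

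Section 11.1 (Surgery) uses the same allocation-based logic for the clips that guide an EBRT boost: "Patients who are not randomised to the TARGIT arm should have the tumour bed localised with two" titanium clips per available face. It does not forbid clips in other patients.

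Four other statements bear on the point:

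- Section 8 (Study design), on timing: "Patient consent is sought and randomisation is carried out prior to" surgical removal of the tumour.
- Section 11.2 (Patient Compliance), on non-receipt: "Some patients will refuse the allocated therapy between randomisation and surgery, but" "based on our experience with more than 3000 patients from the TARGIT A Trial we think the number" will be minimal. No rate is given.
- Section 7 (Trial objectives and purpose), on standard care: "The conventional policy for such a patient is to receive radiation boost to the tumour bed" by external beam, in addition to whole-breast EBRT.
- Section 9 (Inclusion criteria), item 2h, on eligibility through higher local risk: "e.g., those who need a tumour bed boost or those" unsuitable for TARGIT alone.

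**The concern.** A rule tied to the randomised arm works only if every woman receives what she was allocated, and the protocol itself expects that some will not. Refusal is the case it names. TARGIT could also prove undeliverable on the day, because section 11.2 sets conditions at operation: complete haemostasis, an applicator that fits without tension, and skin kept at least 1 cm away.

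Nothing in the document says what boost such a woman then has. A site that follows the sentence literally gives her whole-breast radiotherapy without the boost she would have had outside the trial. A site that gives her an EBRT boost contradicts the wording. In the first case a woman at high risk loses conventional treatment because of her allocation.

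There is also a smaller effect on the trial. Under intention to treat her outcome counts in the TARGIT arm. An avoidable unboosted group raises that arm's recurrence rate and dilutes the superiority contrast more than ordinary crossover to an EBRT boost would.

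**Working it through.** **Does any other text supply a fallback?**

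- Section 11.2 (Preparation of the Intrabeam) allows TARGIT at a later procedure. That is still TARGIT, so it does not help a woman who refuses it or never has it. Section 8 (Changes to protocol) also reports that delayed TARGIT appeared less effective.
- Section 11.2 (Patients with positive margins) bars a further boost to a tumour bed that has already had TARGIT. It is silent on women who have not had it.
- Section 5 permits other adjuvant treatments as needed. This is general, whereas the EBRT boost sentence is specific and says 'only'.
- Sections 13.1, 15.2 and 16.2 require intention to treat. That settles how she is analysed, not how she is treated.

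None of these provides a boost for a woman who never receives TARGIT.

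**Inputs from section 15.1.** Recurrence 5.64% (EBRT boost) and 2.9% (TARGIT boost), two-sided alpha 0.05, power 80%, 1707 patients before attrition, accrual goal 1796 (898 per arm).

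**The plan's own figure.** For a two-proportion test with pooled variance and no continuity correction, with p̄ = (0.0564 + 0.029)/2 = 0.0427:

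n per arm = [1.96·√(2p̄(1−p̄)) + 0.8416·√(p₁(1−p₁) + p₂(1−p₂))]² / (p₁−p₂)² = 853.5

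Rounded up this is 854 per arm, or 1708 in total, against 1707 stated. Power at 853.5 per arm is 80.0%, so the design inputs reproduce.

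**Assumptions not in the protocol.** A share u = 1%, 2% or 5% of the TARGIT arm does not receive TARGIT (898u ≈ 9, 18 or 45 women). Five-year recurrence without a boost is k × 5.64% with k = 1.5 to 2, that is 8.5% to 11.3%.

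**Formulas.**

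- TARGIT-arm rate with an EBRT fallback: (1−u)·2.9% + u·5.64%
- TARGIT-arm rate with no boost: (1−u)·2.9% + u·k·5.64%
- Power: Φ{[|p₁−p₂|·√n − 1.96·√(2p̄(1−p̄))] / √(p₁(1−p₁) + p₂(1−p₂))}, n = 853.5 per arm
- Extra recurrences: 898·u·(k−1)·5.64%

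| u | Rate, fallback | Power, fallback | Rate, no boost (k = 1.5 to 2) | Power, no boost | Cost of the rule (points) | Extra recurrences |
|---|---|---|---|---|---|---|
| 1% | 2.927% | 79.1% | 2.956–2.984% | 78.1–77.1% | 1.0–2.0 | 0.25–0.51 |
| 2% | 2.955% | 78.1% | 3.011–3.068% | 76.1–74.1% | 2.0–4.1 | 0.51–1.01 |
| 5% | 3.037% | 75.2% | 3.178–3.319% | 69.8–64.0% | 5.4–11.2 | 1.27–2.53 |

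The cost column is the difference between the two power columns. It isolates the rule from the loss that any non-receipt causes.

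**Per affected woman:** (k−1) × 5.64% = 2.8 to 5.6 percentage points more absolute risk than with an EBRT boost.

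**Sensitivity.** Suppose the same share of control patients miss their boost, so the control rate is (1−u)·5.64% + u·k·5.64%.

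| u | Power, fallback (k = 1.5 to 2) | Power, no boost (k = 1.5 to 2) | Cost of the rule (points) |
|---|---|---|---|
| 1% | 79.8–80.5% | 78.8–78.6% | 0.9–1.9 |
| 2% | 79.6–80.9% | 77.6–77.1% | 1.9–3.8 |
| 5% | 78.9–82.2% | 73.9–72.7% | 5.0–9.5 |

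The cost falls slightly but does not disappear.

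**The case against.** The best defence is that the sentence only keeps the arms apart. It describes protocol treatment and is meant to stop an EBRT boost being added to TARGIT, for which section 11.2 gives a safety reason. A woman who refuses TARGIT has left her allocated treatment, and a sensible clinician would treat her by local guidelines. The wording is 'should', where firm requirements elsewhere use 'must'. Patients may opt out at any time (section 16.2), and deviations have a form and operating procedures (section 17.3). Site policy statements, those procedures and the trial schema are not visible and might cover the case. Delayed TARGIT narrows the gap, clips are not forbidden in the TARGIT arm, and a surgeon told of a refusal beforehand could place them. The numbers also rest on assumed rates, while the protocol expects few refusals.

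Part of this stands. The gap is confined to women who get TARGIT neither at surgery nor later and who keep the breast. Nothing suggests that the authors meant to leave them unboosted, and many sites would probably do the right thing. The clip point is secondary, and the power figures should not drive the severity.

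It does not remove the problem. Opt-out provisions and deviation forms record what happened but give no treatment path. Documents outside the protocol cannot be relied on to override a specific 'only' within it. The positive-margin rule shows that the authors could write by treatment received; the EBRT boost rule does not. If the intent is as the defence says, the text should say so.

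**Conclusion.** The concern holds. The protocol states a rule here; it is not merely silent. Followed as written, it withholds a conventional boost from a high-risk woman because of an allocation she did not receive. It should be fixed for patient safety, and few women are likely to be affected.

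The effect on the trial is secondary and probably small. The protocol's expectation of minimal refusal points to the 1% row: about 9 women, less than one extra recurrence, and 1 to 2 points of power. The 5 to 11 point loss requires 5% non-receipt with every such woman left unboosted. All of these figures depend on the assumed non-receipt share and the assumed 1.5- to 2-fold risk without a boost; the protocol gives neither. That the text provides no boost for these women does not depend on those assumptions.

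**What to change.** Reword two sentences so that they follow treatment received:

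- **Section 11.2, External beam radiotherapy.** Give the EBRT tumour-bed boost to patients randomised to EBRT boost, and to any patient allocated to TARGIT who did not receive it and still has breast-conserving treatment. Withhold it only from patients who received TARGIT. This agrees with the existing rule against boosting a bed already treated with TARGIT.
- **Section 11.1, Surgery.** Place clips whenever TARGIT is not delivered at that operation and is not planned as a subsequent procedure.

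Keep the intention-to-treat analysis as it is.

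The cost is a short protocol amendment, with no new patients, visits or forms. The drawback is that the few TARGIT non-recipients become crossovers to EBRT boost while still counting in the TARGIT arm. Under the assumptions above, that dilutes the contrast less than leaving them unboosted.
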